Assessment of a Fruit and Vegetable Prescription Program for Children

Trial #: NCT04767282

Study Protocol and Analysis Plan

Submitted: 11/06/2020

Background

The 2020-2025 Dietary Guidelines for Americans state that children and adolescents should consume fruits and vegetables regularly to support healthy development and prevent chronic disease. The US Department of Agriculture recommends a minimum daily intake of 1.5 cups of fruit and 1.5 cups of vegetables for females ages 9-13 years and 1.5 cups of fruit and 2 cups of vegetables for males ages 9-13 years.^{1,2} These recommendations often are unfulfilled, especially within low-income households.³⁻⁸ While most young people across the US struggle to attain even the minimum daily recommendations related to fruit and vegetable consumption,^{7,8} ultra-processed foods now comprise the majority of total energy intake among US youths 2-19 years.⁹ Increased adiposity related to shifts in diet and exercise have prompted public health action to encourage intake of fresh or minimally processed food among children and adolescents.¹⁰

Eating patterns during childhood and adolescence are important to long-term diet and health¹¹⁻¹³ and play a key role in the development of diet-related chronic health conditions.¹³⁻¹⁹ To support healthy food choices while also addressing food access challenges, some health care clinics have introduced fruit and vegetable prescription programs.²⁰⁻²³ The programs differ in design and scope, yet most include health provider-issued prescriptions that patients can exchange, without charge, for fresh produce at local farmers' markets, mobile markets, or food stores. While programs are increasingly available across the country, most target adults with chronic health conditions, offering fruit and vegetable prescriptions as a disease-management strategy.²²⁻²⁵ Few studies have examined whether, and to what degree, exposure to pediatric fruit and vegetable prescription programs influences the diet and health of youth.^{26,27} With childhood and adolescence representing a critical period of development when many are establishing lifelong dietary behaviors,¹¹⁻¹³ these programs are likely to have meaningful health implications.

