This study will include a cross-sectional analysis of data from a consecutive sample of caregiver-child dyads with varying levels of exposure to a fruit and vegetable prescription program (FVPP) that provides one \$15 prescription for fresh produce to every child during pediatric office visits. Considering the importance of dietary patterns during childhood on long-term diet and health¹¹⁻¹³ alongside evidence that indicates adolescence is the specific period when food insecurity has the greatest potential to negatively impact the diet,³⁵ data collection and analyses will focus specifically on children and adolescents ages 8-16 years. A total of 700 caregiver-child dyads (one caregiver and one child per household) will be enrolled in the study, with approximately 200 dyads enrolled at clinic 1 (high exposure); 200 dyads enrolled at clinic 2 (moderate exposure), and 300 dyads enrolled at clinic 3 (no previous exposure to the FVPP). A description of the clinics is provided with our explanation of the 'Setting' for this study.

Dyad enrollment will be based on exposure to the FVPP as defined by caregiver-reported and clinic-verified length of time that the participating child has been a patient at one of three partnering clinics. Accordingly, we expect dyads to cluster based on pediatric clinics as follows: clinic 1 (high exposure), clinic 2 (moderate exposure), and clinic 3 (no previous exposure). A sample of approximately 200 pediatric patients newly exposed to the FVPP at clinic 3 will be followed for a period of two years as part of a non-controlled longitudinal intervention trial that will examine changes in dietary patterns, food security, and weight status over time.

Setting

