Flint, Michigan, is a low-income urban city where an approximate 60% of children live in poverty, and full-service grocery stores located inside the city are limited.³⁶ The city lacks resources and nutritional options, like many low-income urban cities in the US. As a result, many children consume insufficient nutrient-dense foods and excessive poor-quality, calorie-dense foods.²⁰ Local stores in Flint tend to offer lower-quality foods and fewer healthy foods than offered in higher-income neighborhoods.^{28,37-39} Along with long-lasting issues related to food access and affordability coupled with recovery from a drinking water crisis,⁴⁰ the SARS-CoV-2 coronavirus pandemic has disproportionately affected Flint and surrounding Genesee County. Confirmed COVID-19 case prevalence has consistently placed the county in the top ranks (#5) among 83 Michigan counties. In ordinary times, with constrained wealth, and many families in poverty, under- or unemployed, Flint faces extraordinary health challenges. The pandemic has compounded these ordinary challenges, with results that include more hungry children and increased food insecurity.

The current study will occur at three clinics in Flint serving demographically similar patient populations.

- Clinic 1 is a university-affiliated pediatric clinic that introduced Michigan's first pediatric fruit and vegetable prescription program. The program began as a pilot in February 2016. After several program iterations and refinements, all patients currently receive one \$15 prescription for fresh fruits and vegetables at every office visit. Pediatricians at clinic 1 have distributed approximately 40,000 prescriptions since the FVPP was introduced.
- Clinic 2 is one of the largest private-practice pediatric clinics in Flint, serving over 3,000 young patients. The FVPP was introduced at clinic 2 in August 2018 as part of a grant to assess the feasibility and preliminary effectiveness of the FVPP at a second clinic site.²⁶ Clinic 2 was selected for this expansion because of the clinic size, demographics of the patient population which closely match clinic 1, and use of an electronic medical record (EMR) system that is identical to clinic 1 (allowing easy tracking of monthly prescription distribution rates). Clinic 2 has distributed over 15,000 prescriptions since August 2018.

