To monitor prescription redemption, FFM vendors will collect paper prescriptions redeemed for fresh produce and turn them into the FFM management office at the end of each month for payment. Prescriptions will be collected, sorted, stored, and entered into a database for tracking purposes. A similar method will be used to track and record monthly prescription redemption through Flint Fresh, including tracking of virtual prescriptions which were introduced during the COVID-19 pandemic as pediatric telehealth visits increased.

Data collection procedures

Consent/assent procedures and data collection at baseline will be carried out in a private clinic location, such as a patient examination room. A trained research assistant (RA) will follow our study's Institutional Review Board (IRB)-approved protocol for consent, child assent, and data collection (e.g., of dietary data). The RA will provide detailed instructions regarding the study, survey completion, and how to make use of an iPad and its interface with a secure digital platform (Research Electronic Data Capture or REDCap). Researchers will copy the signed consent and assent forms at pediatric offices and provide to families upon enrollment in the study or researchers will email copies of signed e-consent and assent and provide to families upon enrollment in the study. Caregivers and children will be told that their participation is voluntary; that they may stop participating at any time; that they may choose how much information they feel comfortable sharing; that their individual identity will not be shared with anyone; and that in the writing of any results, pseudonyms will be used. Families will be told by researchers as well as pediatricians and office staff that their acceptance or refusal to participate in the research study will not impact their eligibility to receive the fruit and vegetable prescription. Each member of the caregiver-child dyad will separately complete a standardized questionnaire with pre-worded demographic and pilot-tested survey questions that assess dietary patterns, food security, and food access.²⁰ The RA will assist children with survey completion. Child body mass index (BMI) percentile and BMI z-score will be calculated based on measured height and weight, as described in the 'Primary Outcome Measures' section. Key constructs and study measures are listed in Table 1.

Table 1. Key Constructs

Domains	Constructs	Measures	Instruments

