To compare baseline dietary intake, food security, and weight status between pediatric patients with varying levels of exposure to the FVPP, we will collect study measures at baseline from 700 dyads at each of three partnering clinics. To measure changes in diet, food security, and weight status when never-exposed children are introduced to the FVPP, we will follow approximately 200 dyads from clinic 3, collecting study measures at baseline, 12- and 24-month follow-up. In addition to posters, brochures, and websites that explain the FVPP, caregivers at clinic 3 will be reminded of each follow-up visit through reminder cards and telephone calls.

REDCap provides data security measures designed to prevent unauthorized access, disclosure, alteration, and use of data. Data from the completed evaluation tools will be stored in REDCap project database. Children and caregivers will be assigned identification numbers upon enrollment in the study. All data will be de-identified within the data management system, and de-identified data will be exported for analyses.

Any modifications to the approved protocol will be submitted to Michigan State University IRB for review and approval prior to implementation. Furthermore, although the likelihood of any adverse event in this trial is remote, we have formalized our Data and Safety Monitoring Plan to include a designated Data and Safety Monitor. This Monitor will have the authority to recommend termination of the trial if he makes the determination that unacceptable adverse events have taken place. Should any adverse events occur, these will be immediately reported to Michigan State University IRB for review.

Benefits

Completion of our study aims will provide empirical evidence for the effectiveness of Produce Prescription Programs, which were recently added to the US Farm Bill through the Gus Schumacher Nutrition Incentive Program. Our study will share insights regarding the duration and intensity of exposure necessary to influence changes in food security, dietary patterns, and weight status when fruit and vegetable prescriptions are provided to pediatric patients. Furthermore, our results will be especially important to pediatricians and primary care physicians who recognize the consequences of food insecurity among young patients and are seeking tangible solutions that not only provide food to hungry children but ensure that the food provided is high in nutrients needed to support healthy growth and development.

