After baseline data collection, periodic follow-up assessments will be conducted to study changes in diet, food security, and weight status among children newly exposed to the FVPP at clinic 3. Because of the repeated nature of the data generated for this aim, we will consider methods that accommodate the within-child and/or the within-caregiver association. For continuous outcomes (e.g., dietary intake), repeated measures models such as linear mixed models and repeated ANOVA models, will be entertained in view of their robustness to certain types of missing data. These classes of models will be used to assess changes from baseline at key points in the study.^{63,64} For ordinal endpoints such as food security (with ordered levels), a generalized linear mixed effects model with cumulative logits will be entertained. To examine whether there is a significant improvement in child-reported food security from baseline, contrast representing the difference in log-odds between baseline and follow-up will be evaluated. Alternatively, GEE counterparts of these likelihood-based models (that use the sandwich-based correction in lieu of the model-based variance-covariance matrix of the parameter estimates) will also be considered.⁶⁵

Comparison of mean follow-up measures in the initial no exposure group to baseline measures in the high exposure group

At follow-up, measures of dietary intake, food security, and weight status in a group of children newly exposed to the FVPP will be compared to baseline measures of children with high exposure to the FVPP (>24 months). For example, to compare measures of dietary intake (at 12 months and 24 months) in the newly exposed group to those of the highly exposed group, the class of linear mixed models and repeated ANOVA models will be considered. These models will be similar to those of aim 2, with the additional flexibility of group-specific time-point effects. For ordinal outcomes (e.g., food security) and binary outcomes (e.g., obesity), a generalized linear mixed effects model will be used. Alternative models such as GEE models will also be entertained.

Discussion

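### Neither the clinic 3 before-after comparison (Aim 2) nor the clinic 3 follow-up versus clinic 1 baseline comparison (Aim 3) can separate the programme from change over calendar time, in either direction

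*Combined protocol and SAP*

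**What the plan says.** Study Design describes the clinic 3 follow-up as a "non-controlled longitudinal intervention trial that will examine changes in dietary patterns, food security, and weight status over time". Under Data collection procedures, about 200 clinic 3 dyads are measured at baseline, 12 and 24 months. No follow-up is scheduled at clinics 1 and 2.

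The Setting section writes of the pandemic as current: "the SARS-CoV-2 coronavirus pandemic has disproportionately affected Flint and surrounding Genesee County", "with results that include more hungry children and increased food insecurity". Child-reported and household food security both stand under Primary outcome measures. The programme section notes that delivery also changed, with "virtual prescriptions which were introduced during the COVID-19 pandemic as pediatric telehealth visits increased".

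For Aim 2, the SAP uses repeated-measures models of change from baseline by visit, and asks "whether there is a significant improvement in child-reported food security from baseline". For Aim 3, it compares clinic 3 at 12 and 24 months with clinic 1 at baseline, in similar models with time-point effects that may differ by group. The adjustment variables named for the baseline comparison are child, caregiver and household characteristics. The list is introduced as examples, and the SAP also plans to look for further confounders.

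On interpretation, Benefits says: "Completion of our study aims will provide empirical evidence for the effectiveness of Produce Prescription Programs". The Discussion makes a similar statement.

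**The concern.** The plan names a shock to one of its own primary outcomes, in its own city, and does not return to it as a possible explanation of later change. In a single cohort, time since introduction of the programme and time since the shock advance together. Regression adjustment and the generalized propensity score deal with differences between groups; they do not remove a trend within clinic 3. Time-point effects in the Aim 3 model are visit effects, so they do not repair the 12- or 24-month gap between the clinic 3 follow-up and the clinic 1 comparator.

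Aim 1 is less exposed, because all three clinics are measured at baseline. But the plan does not say that they enrol over the same months.

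At stake is what a significant change, or the lack of one, may be taken to mean. Sampling error and power do not bear on this: a larger cohort would detect a secular change more reliably and attribute it no better.

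**Working it through.** **The plan's own figures.** The plan gives no figure for secular change. Its inputs for the 12-month change (Participants and recruitment) are mean 0.72 cup, SD 0.77 cup, target 0.90 cup, correlation 0.2 and two-sided alpha 0.05. The dispersion reproduces: 0.77²/0.72 = 0.82. The power for 300 dyads does not quite. Var(difference) = 0.82 × (0.72 + 0.90) − 2 × 0.2 × 0.82 × √(0.72 × 0.90) = 1.064; SE = √(1.064/300) = 0.0596; z = 0.18/0.0596 = 3.02; power = Φ(3.02 − 1.96) = 86%, where the plan says well above 90%. That is a separate matter and nothing below depends on it.

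**How often background change alone is significant.** Assumptions, none from the documents: no programme effect, food insecurity 50% at baseline, background falls of 5 or 10 points, correlation 0.2 to 0.5, and a paired test of a binary outcome in place of the planned ordinal model. SE = √(2 × 0.25 × (1 − ρ)/n); chance of a significant improvement = Φ(fall/SE − 1.96).

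The household scale applies to all 200 followed dyads. The child module is completed only from age 12. If ages are spread evenly over 8 to 16 (assumed), 5 of 9 single years qualify: 200 × 5/9 ≈ 111 pairs.

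| Pairs | Background fall | ρ = 0.2 | ρ = 0.5 |
|---|---|---|---|
| 200 (household) | 5 points | SE 0.0447, z 1.12: 20% | SE 0.0354, z 1.41: 29% |
| 200 (household) | 10 points | z 2.24: 61% | z 2.83: 81% |
| 111 (child) | 5 points | SE 0.0600, z 0.83: 13% | SE 0.0475, z 1.05: 18% |
| 111 (child) | 10 points | z 1.67: 38% | z 2.11: 56% |

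With no background change the chance would be 2.5% in this direction. A background rise of the same size would hide a programme benefit of that size.

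Vegetable intake is less sensitive. With 200 pairs, SE = √(2 × 0.77² × (1 − ρ)/200) = 0.069 or 0.054 cup. An assumed drift of 5% (0.036 cup) is significant in 8-10% of studies, and one of 10% (0.072 cup) in 18-26%.

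**What a calendar-date term could recover.** Within a child, assessment date is enrolment date plus visit time, so a calendar slope is estimated only from differences in enrolment date between children. Take a linear trend common to the three clinics, enrolment spread evenly over W months in each, three exchangeable visits with ρ = 0.2, 200 followed and 100 baseline-only dyads at clinic 3, and 200 baseline dyads at each of clinics 1 and 2.

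- Information on the slope = (W²/12)/0.77² × (200 × 3/1.4 + 100 + 200 + 200) = (W²/12) × 928.6/0.5929.
- Unadjusted SE of the intake change at either visit = 0.064 cup (using all 300 clinic 3 baselines).
- Adjusted SE at h months = √(0.064² + (h × SE of slope)²).

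| Enrolment window W | SE of slope per month | SE at 12 months | SE at 24 months |
|---|---|---|---|
| 6 months | 0.0146 | 0.19 | 0.36 |
| 12 months | 0.0073 | 0.11 | 0.19 |
| 24 months | 0.0036 | 0.08 | 0.11 |

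The planned difference is 0.18 cup. With a 12-month window the 95% half-width is 1.96 × 0.1085 = 0.21 cup at 12 months. With a 6-month window it is 1.96 × 0.356 = 0.70 cup at 24 months.

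**The case against.** The plan is partly candid. It calls the follow-up non-controlled and words Aim 2 as change before and after introduction. The effectiveness statements stand in Benefits and Discussion and refer to completing the aims together. The adjustment list is open, so a calendar term is not excluded. All of this stands, and it limits the point to something the plan leaves unsaid: no model names calendar time, and no text warns that change in Aims 2 and 3 includes secular change.

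A reader might infer more than the documents support:

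- That baseline falls in the pandemic. No enrolment dates are given. The title page says "Submitted: 11/06/2020" while the reference list has access dates in November 2021, so even the date of writing is unclear. The inference is reasonable but remains an inference.
- That the bias favours the programme. This needs recovery by 12 or 24 months, which no section states. Worsening would bias the result the other way.
- That calendar time and exposure are completely confounded. Staggered enrolment separates them in part, at the cost shown.
- That the plan claims effectiveness from Aim 2 alone. It does not say so in those words.
- That the clinics will enrol in different months. The plan is silent, and nothing suggests it.

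**Conclusion.** The point holds as a limit on interpretation. Aims 2 and 3, as specified, estimate programme effect plus secular change, and the plan gives no means of telling them apart. This follows from the design and does not depend on the enrolment dates. The pandemic makes it material, because the plan itself reports an effect on food security.

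The size of the risk is illustrative. It rests on assumed background changes, a 50% starting prevalence and a binary simplification; the 200-pair figures apply to the household scale only. The direction of any bias is unknown. Calendar adjustment is a partial check that relies on a linear, shared trend, and cannot replace the main analysis.

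**What to change.** 1. In Benefits, the Aim 2 and Aim 3 parts of the SAP, and the Discussion, state that these aims estimate change over time that includes secular change in either direction, and that no effectiveness conclusion will rest on them alone.
2. In Participants and recruitment, state that the three clinics enrol over the same calendar months. Add calendar month of assessment to the Aim 1 adjustment list.
3. For Aims 2 and 3, add a sensitivity analysis with a linear calendar-date term, partly identified by staggered enrolment and the three clinics' baseline dates. Report it beside the main estimate and state the enrolment window.

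The cost is wording, scheduling of enrolment and one extra model, with no added participants or visits. The plan exports de-identified data and does not say whether dates are kept, so assessment date must be retained in the analysis file. The drawbacks are a less favourable claim and much wider intervals in the sensitivity analysis, which may say little at 24 months if enrolment is short.

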- Clinic 3 is the largest pediatric clinic in Genesee County, with Flint as its urban center. Expansion of the FVPP to clinic 3 will substantially increase program reach among vulnerable children and families living in Flint. Last year, clinic 3 had over 12,000 pediatric visits. It has a comparable patient population to clinics 1 and 2, serving only children in need who are residents of Genesee County.

Participants and recruitment

A sample of 250 caregiver-child dyads presenting at clinic 1, 250 caregiver-child dyads at clinic 2, and 350 caregiver-child dyads at clinic 3 will be assessed for eligibility, with 700 total dyads enrolled (anticipated 10-15% not meeting eligibility and 10% refusal based on a previous study). To control for confounders, we will adopt a balancing strategy that consists of recruiting in the study children who have approximately the same age, sex, and race across the three clinical settings. These children will not be balanced according to variables pertaining directly to the exposures (e.g., duration of FVPP exposure).

With target samples of 200, 200, and 300 caregiver-child dyads enrolled in clinic 1 - high exposure, clinic 2 - moderate exposure, and clinic 3 - no previous exposure, respectively, we have well above 90% power to jointly detect modest relative differences in the baseline mean intake of vegetables of 20% from clinic 2 to clinic 3 and 38% from clinic 1 to clinic 3. This calculation assumes an underdispersed Poisson model with a dispersion parameter of 0.82, derived using previously published data on the mean intake of vegetables of 0.72 cup and a standard deviation of 0.77 cup in the settings with no prior FVPP exposure.²⁰ Likewise, with 300 caregiver-child dyads enrolled in clinic 3, we have well above 90% power to detect a modest temporal improvement in the mean intake of vegetables of 25% over 12 months (0.72 cup at baseline versus 0.90 cup at 12-month follow-up). This calculation assumes a correlated Poisson model for underdispersed count data with timepoint dispersion parameter of 0.82, and a modest temporal correlation of 0.2. Increasing values of the temporal correlation greatly improves the statistical power. Finally, estimation of FVPP effects will specify two-tailed tests with alpha set at the 0.05 level.

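### At clinic 3 the 350 dyads to be assessed do not yield the 300 to be enrolled: the plan's own loss rates give about 263 to 284

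*Combined protocol and SAP*

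**What the plan says.** Under 'Participants and recruitment' the plan sets 250 dyads to be assessed at each of clinics 1 and 2. For clinic 3, and for the study as a whole, it says: "350 caregiver-child dyads at clinic 3 will be assessed for eligibility, with 700 total dyads enrolled (anticipated 10-15% not meeting eligibility and 10% refusal"). The number assessed is thus 250 + 250 + 350 = 850. The plan takes its refusal rate from earlier work, and no clinic has loss rates of its own.

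The enrolment targets are 200, 200 and 300. 'Study Design' gives about "300 dyads enrolled at clinic 3 (no previous exposure to the FVPP"), and the power paragraph uses that number as an input: "with 300 caregiver-child dyads enrolled in clinic 3, we have well above 90% power" for the 12-month change in vegetable intake. The Aim 1 power statement also takes 300 at clinic 3.

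'Study Design' and 'Data collection procedures' both say that approximately 200 clinic 3 dyads will be followed over two years. 'Data collection procedures' also says that baseline measures will come "from 700 dyads at each of three partnering clinics", whereas 'Study Design' makes 700 the total for the study.

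**The concern.** The numbers assessed, the losses and the numbers enrolled are tied by simple multiplication, and at clinic 3 they do not agree. The loss that the plan implies is 20% at clinics 1 and 2 (250 to 200), which fits its stated rates. At clinic 3 it is 14.3% (350 to 300), which does not.

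Clinic 3 supplies the unexposed group for Aim 1 and is the only source of the longitudinal cohort for Aims 2 and 3. If assessment stopped at 350, the unexposed group would be smaller than the one on which both power statements rest.

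**Working it through.** **Inputs** (all from 'Participants and recruitment'): assessed 250/250/350; ineligible 10-15%; refusal 10%; targets 200/200/300.

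**Share retained.** The plan does not say whether refusal is a share of those eligible (sequential losses) or of those assessed (additive losses), so both are shown.

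- Sequential: 0.90 × 0.90 = 0.81; 0.85 × 0.90 = 0.765.
- Additive: 1 − 0.10 − 0.10 = 0.80; 1 − 0.15 − 0.10 = 0.75.

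The combined loss is therefore 19% to 25%.

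**Enrolled = assessed × share retained**

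| Losses | 250 assessed (target 200) | 350 assessed (target 300) | 850 assessed (target 700) |
|---|---|---|---|
| Sequential, 10% ineligible | 202.5 | 283.5 | 688.5 |
| Additive, 10% ineligible | 200.0 | 280.0 | 680.0 |
| Sequential, 15% ineligible | 191.3 | 267.8 | 650.3 |
| Additive, 15% ineligible | 187.5 | 262.5 | 637.5 |

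The plan's 200 is reproduced at clinics 1 and 2 with 10% ineligible. Its 300 at clinic 3 is not reproduced in any row; the gap is 5.5% to 12.5%. The total is 1.6-2.9% short at 10% ineligible and 7.1-8.9% short at 15%.

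**What would give 300 from 350?** Leaving refusal out at 15% ineligible comes close (350 × 0.85 = 297.5). With 10% ineligible, refusal among those eligible would have to be 1 − 300/(350 × 0.90) = 4.8%. The text supports neither.

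**Numbers to assess = target / share retained, rounded up**

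- Clinics 1 and 2: 200/0.81 = 247 to 200/0.75 = 267 each.
- Clinic 3: 300/0.81 = 371 to 300/0.75 = 400.
- Total: 865 to 934.

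**Effect on power, Aim 2.** Means 0.72 and 0.90, variance 0.82 × mean, correlation 0.2, two-sided 0.05, complete follow-up. The variances are 0.590 and 0.738. The SD of the difference is √(0.590 + 0.738 − 2 × 0.2 × √(0.590 × 0.738)) = 1.032. Power = Φ(0.18 × √n / 1.032 − 1.96).

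- n = 300: 86%
- n = 284: 84%
- n = 268: 81%
- n = 263: 81%

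Working with log means instead gives 85%, 83.5%, 81% and 81%. The loss due to the shortfall is about 2 to 5 points.

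**Effect on power, Aim 1.** I read the 20% and 38% as increases over 0.72, so the means are 0.9936, 0.864 and 0.72. For a 2-df test on log means, with weights w = n × mean / 0.82, the noncentrality is Σw(log mean − weighted average)². With clinics 1 and 2 at 200:

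- clinic 3 at 300: 13.21, power 91%
- at 284: 12.83, 90%
- at 268: 12.44, 89%
- at 263: 12.31, 89%

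The loss is about 1 to 2 points. If all three clinics fell to their lowest yield (188/188/263), the same formula gives 11.97 and 88%, a loss of about 3 points.

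**The case against.** The best defence is that 350 need not be a hard stop. The plan describes a consecutive sample, calls 200/200/300 targets and attaches an approximation to them, and clinic 3 has over 12,000 visits a year. Much of this stands: under-enrolment is not shown to be inevitable. But no section says that assessment continues past 350. Nor does any section give lower losses at clinic 3. The eligibility criteria name further exclusions for that clinic (an enrolled sibling; movement between clinics, under 3%). An approximate target does not absorb a gap of 5.5-12.5% when 300 is then used as an exact power input.

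A reader might infer three stronger things, none of which the documents support.

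- **The longitudinal aim cannot be filled.** About 200 dyads are to be followed, and even 263 exceeds that by 63. The margin over 200 narrows from 100 to 63-84, but it does not vanish.
- **The shortfall is what takes Aim 2 power from over 90% down to 81-84%.** By the calculation above, power is already about 85-86% at 300, so most of that gap has another source. Whether 300 is the right number for Aim 2, when about 200 are to be followed, is a separate question.
- **All clinics and the total clearly miss their targets.** At 10% ineligibility, clinics 1 and 2 reach 200-203 and the total reaches 680-689.

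The phrase about 700 dyads at each clinic is best read as a wording slip, since 'Study Design' and 'Participants and recruitment' both give 700 in total. It adds no weight to the screening arithmetic.

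**Conclusion.** The plan is wrong as written at clinic 3. Under its own loss rates, 350 assessed yields about 263-284 dyads, which is 16 to 37 short of the 300 used in both power statements. This holds whether the losses are sequential or additive and at either end of the ineligibility range. It assumes that the stated rates apply equally at each clinic and that 350 is the number actually assessed.

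At clinics 1 and 2 (188-203 against 200) and in total (638-689 against 700), the plan is on or near target at 10% ineligibility and clearly short only towards 15%.

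The consequence is modest: about 2-5 points of power for Aim 2, and 1-2 for Aim 1 with clinics 1 and 2 at target. The power figures rest on a normal approximation with the plan's dispersion and correlation. This is an inconsistency in recruitment planning that should be corrected. It does not threaten the design.

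**What to change.** Choose one of three.

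1. State that consecutive assessment continues until 200, 200 and 300 dyads are enrolled, and drop the fixed 250/250/350. This is the simplest repair and leaves the targets unchanged.
2. Keep fixed numbers but correct them to about 247-267, 247-267 and 371-400, or 865-934 in total. At the upper end that is 934 − 850 = 84 more eligibility checks: 50 at clinic 3 and 17 at each of the others.
3. If 350 is a true cap at clinic 3, restate enrolment there as about 263-284 and recompute both power statements at that size.

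If lower losses are expected at clinic 3, give the clinic-specific rates and their source.

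Separately, reword the sentence in 'Data collection procedures' so that 700 is the total across the three clinics.

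The first option costs one sentence, and the second costs that plus the extra checks, which are few beside clinic 3's yearly visits. The third costs a short recalculation.
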